**1.0 GOALS AND OBJECTIVES (SCIENTIFIC AIMS)****1.1 Primary Aims**

- 1.1.1 To determine the recommended phase 2 dose (RP2D) or the maximum tolerated dose (MTD) of the tablet formulation of selinexor in children with recurrent/refractory solid and CNS tumors.
- 1.1.2 To describe the toxicities of selinexor in children with recurrent/refractory solid and CNS tumors.
- 1.1.3 To characterize the pharmacokinetics of the tablet formulation of selinexor in children with recurrent/refractory solid and CNS tumors.

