## 5.0 TREATMENT PROGRAM

### 5.1 Treatment Overview (Pre-Amendment #1):

Week	Day	Agent: Selinexor
1	1, 3 (Doses 1,2)	X
2	8, 10 (Doses 3,4)	X
3	15, 17 (Doses 5,6)	X
4	22, 24 (Doses 7,8)	X

Patients will receive selinexor twice weekly on a days 1,3 schedule (Mon/Wed, Tues/Thurs, or Wed/Fri). A cycle of therapy will be 28 days or 8 doses. The drug will be administered in tablet form with food. Patients may continue for a maximum of 24 cycles. Refer to [section 7.3](#) for recommended supportive care guidelines.

(Amendment #1):

Week	Day	Agent: Selinexor
1	1, 3 (Doses 1,2)	X
2	8, 10 (Doses 3,4)	X
3	15, 17 (Doses 5,6)	X
4	Rest	

With Amendment #1, patients will receive selinexor twice weekly on a days 1,3 schedule (Mon/Wed, Tues/Thurs, or Wed/Fri) on Weeks 1-3, followed by a one-week rest period. A cycle of therapy will be 28 days or 6 doses. The drug will be administered in tablet form with food. Patients may continue for a maximum of 24 cycles. Refer to [section 7.3](#) for recommended supportive care guidelines.

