**Amendment #4:**

Week	Day	Agent: Selinexor
1	1	X
2	8	X
3	15	X
4	22	X

With Amendment #4, patients will receive selinexor once weekly, on Days 1, 8, 15, and 22 of a 28-day cycle. The drug will be administered in tablet form with food. Patients may continue for a maximum of 24 cycles. Refer to [Section 7.3](#) for recommended supportive care guidelines.

Drug doses should be adjusted based on the BSA calculated from height and weight measured within 7 days prior to the beginning of each cycle (See [Appendix VI](#)). If a dose is vomited within 30 minutes of administration and there is visible evidence of the tablet, the dose should be repeated. If the tablet is not visible, or the dose is vomited later than 30 minutes after administration, the dose should not be repeated. The patient/caregiver should make a note of the vomited dose and whether there is visible evidence of the tablet on the pill diary and proceed with the next dose at the next scheduled time of administration.

Selinexor is supplied by Karyopharm Therapeutics. **Do not use commercial supply.**

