### 8.3.2 Sampling Schedule

Blood samples will be obtained at the time points specified in [Appendix III](#) and just before tumor resection for patients on part C.

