**APPENDIX III: PHARMACOKINETIC STUDY FORM**

COG Pt ID # \_\_\_\_\_ ACC # \_\_\_\_\_

Please do not write patient names on this form or on samples.

Cycle 1, Day 1 Date: \_\_\_/\_\_\_/\_\_\_/\_\_\_/\_\_\_ Dose Level: \_\_\_\_\_mg/m^2 Dose Administered: \_\_\_\_\_mg

Plasma samples (1 mL) will be collected for pharmacokinetic studies at the time points listed in the table below. Record the exact date and time each sample is drawn and the time of the selinexor administration. In the event the dose is vomited within 30 minutes after administration on Cycle 1, Day 1 **and** there is no visible evidence of the tablet, the PK samples #2-9 should be collected after the second dose on Cycle 1, Day 3.

Blood Sample No.	Barcode # (from Sample Label)	Time Point	Scheduled Sample Collection Time	Scheduled Selinexor Time Point	Actual Date Sample Collected or Dose Given	Actual Time Sample Collected or Dose Given (24-hr clock)
1		Cycle 1, Day 1	Prior to Dose on Cycle 1, Day 1		___/___/___	__:__:__
				Cycle 1, Day 1	___/___/___	__:__:__
2		Cycle 1, Day 1	30 min. after Day 1 dose		___/___/___	__:__:__
3		Cycle 1, Day 1	1 hour after Day 1 dose		___/___/___	__:__:__
4		Cycle 1, Day 1	2 hour after Day 1 dose		___/___/___	__:__:__
5		Cycle 1, Day 1	3 hour after Day 1 dose		___/___/___	__:__:__
6		Cycle 1, Day 1	4 hour after Day 1 dose		___/___/___	__:__:__
7		Cycle 1, Day 1	6 hour after Day 1 dose		___/___/___	__:__:__
8		Cycle 1, Day 1	8 hour after Day 1 dose		___/___/___	__:__:__
9		Cycle 1, Day 2	24 (± 2) hr after Day 1 dose		___/___/___	__:__:__

Part C: An additional PK sample will be collected after 2 doses prior to Tumor Resection. Surgical resection should occur after dose on Day 8 but before dose on Day 15 of Cycle 1.

Blood Sample No.	Barcode # (from Sample Label)	Time Point	Scheduled Sample Collection Time	Scheduled Tumor Resection Date	Actual Date Sample Collected or Date of Resection	Actual Time Sample Collected or Dose Given (24-hr clock)
10		After 2 doses	Prior to Tumor Resection		___/___/___	__:__:__
				___/___/___	___/___/___	__:__:__

Refer to [Section 8.3](#) processing and shipping details. One copy of this Pharmacokinetic Study Form should be uploaded into RAVE.

If this form will be used as a source document, the site personnel who collected the samples must sign and date this form below:

Signature: \_\_\_\_\_

Date: \_\_\_\_\_

THIS PROTOCOL IS FOR RESEARCH PURPOSES ONLY, SEE PAGE 1 FOR USAGE POLICY

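### Appendix III moves PK samples 2 to 9 to a Cycle 1 Day 3 dose that the weekly schedule no longer has, so the vomiting fallback cannot be followed as written

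*Combined protocol and SAP*

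**What the plan says.** Primary aim 1.1.3 is "To characterize the pharmacokinetics of the tablet formulation of selinexor in children with recurrent/refractory solid and CNS tumors". For timing, Section 8.3.2 defers to the form: "Blood samples will be obtained at the time points specified in" Appendix III, with one extra pre-resection sample in Part C.

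The fallback in Appendix III has two conditions, both required. The first is "In the event the dose is vomited within 30 minutes after administration on Cycle 1, Day 1"; the second is that "there is no visible evidence of the tablet". When both hold, "the PK samples #2-9 should be collected after the second dose on Cycle 1, Day 3".

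On dosing, the current text of Section 5.1 (Amendment #4) is that "patients will receive selinexor once weekly, on Days 1, 8, 15, and 22 of a 28-day cycle". The superseded text in the same section reads "With Amendment #1, patients will receive selinexor twice weekly on a days 1,3 schedule", under which the second dose did fall on Day 3. Section 5.1 also says that a dose vomited with no visible tablet is not repeated and that the patient goes on to the next scheduled dose. The Appendix VII diary has selinexor entries on Days 1, 8, 15 and 22 only.

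**The concern.** The fallback joins an ordinal (second dose) to a calendar day (Day 3). These agreed under twice-weekly dosing and disagree under weekly dosing. The Part C paragraph of the same form already uses Days 8 and 15, so the line looks like an incomplete update for Amendment #4.

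At stake is the first-dose profile of each patient who meets the trigger. Samples 2 to 9 carry the absorption phase, the peak and the decline; only the pre-dose sample is unaffected. Section 11.5 plans a descriptive summary of exposure and clearance and states no rule for when a profile is evaluable, so a mistimed one has no stated route out of the summary.

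The layout adds to the difficulty. The form has a single dose row, for Cycle 1 Day 1, and describes all of samples 2 to 9 relative to the Day 1 dose. A site that correctly samples after a later dose has no row for its time. Section 8.3.4 warns that handwritten changes to the pre-printed labels are lost at scanning.

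**Working it through.** The plan gives no figure to reproduce here. The check is a comparison of schedules, followed by a short carry-over calculation.

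**1. Is Day 3 a dosing day?**

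| Schedule (Section 5.1) | Dosing days in the cycle | Day 3 dose? | Second dose |
|---|---|---|---|
| Before Amendment #1 | 1, 3, 8, 10, 15, 17, 22, 24 | Yes | Day 3 |
| Amendment #1 | 1, 3, 8, 10, 15, 17 | Yes | Day 3 |
| Amendment #4 (current) | 1, 8, 15, 22 | No | Day 8 |

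**2. How much of the profile moves?** Samples 2 to 9 are 8 of the 9 samples in Parts A and B, and 8 of 10 in Part C.

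**3. What would each reading yield?** Assume first-order elimination, so that the fraction of absorbed drug left at time t is 0.5^(t / half-life). The half-life inputs are about 6 h (Section 2.7, the Amendment #1 rationale), and 7.2 h and 7.9 ± 4.1 h for this trial's patients at 20 and 35 mg/m² (Section 2.8, Table A). As an upper case, 7.9 + 4.1 = 12.0 h.

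Reading by day, first draw at about 48 h with no new dose:
- 6 h: 0.5^(48/6) = 0.0039, or 0.4%
- 7.2 h: 0.5^(48/7.2) = 0.0098, or 1.0%
- 7.9 h: 0.5^(48/7.9) = 0.0148, or 1.5%
- 12.0 h: 0.5^(48/12) = 0.0625, or 6.3%

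These are fractions of whatever was absorbed before vomiting. No absorption phase is sampled, so peak, time to peak, AUC and clearance could not be estimated.

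Reading by ordinal, sampling after the Day 8 dose, 7 × 24 = 168 h after Day 1:
- 6 h: 0.5^(168/6) = 3.7 × 10⁻⁹
- 7.9 h: 0.5^(168/7.9) = 4.0 × 10⁻⁷
- 12.0 h: 0.5^(168/12) = 6.1 × 10⁻⁵

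Carry-over is below 0.01% throughout, so a Day 8 profile would be about as clean as a first-dose profile.

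**4. How many patients?** This cannot be computed. The documents give no rate of vomiting within 30 minutes with no visible tablet.

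**The case against.** The strongest reply is that only half of the instruction is stale. The second dose still exists, Section 5.1 sends the patient to it, and step 3 shows that a profile taken then is sound. A sensible site would sample on Day 8 and lose nothing. This stands against any claim that affected patients yield no usable data, which a reader might infer from the contradiction; the documents say no such thing. It does not make the line workable, because a site must still decide which half to ignore and nothing in Section 8.3 tells it.

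A second reply is that a Day 3 draw would be noticed. Sample times are defined from a dose, exact dose and sample times must be recorded (Section 8.3.3 and the form), and vomited doses are noted in the diary, which is uploaded weekly in Cycle 1. This also largely stands. A near-zero curve passing unnoticed as low exposure is possible but not the likely outcome. Noticing the error, however, does not recover the profile.

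A third reply concerns frequency. Section 7.3.2.1 describes acute emesis, meaning within 24 hours, as infrequent. The trigger is a subset of that, and antiemetic prophylaxis is strongly recommended in Cycles 1 and 2. This stands and limits the weight of the point. It would be wrong to read the line as covering every vomited Day 1 dose: with a visible tablet the dose is repeated, and for vomiting after 30 minutes the form gives no sampling fallback at all.

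Finally, a reader might set one lost profile against the up to 6 patients added for PK (Section 11.1) and call it 1/6, or 17%, of the data. That denominator is too narrow. Section 8.3 makes PK required, and Appendix II lists it for Parts A, B and C.

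**Conclusion.** The contradiction is certain: it follows from the text of Appendix III, Section 5.1 and Appendix VII and needs no assumption. The fallback for a primary-aim profile cannot be followed as written on the weekly schedule. The supported consequence is that profiles meeting the trigger may be missed or mistimed, with 8 of 9 samples at risk per patient in Parts A and B.

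The 0.4% to 1.5% residual applies only to a site that goes by the calendar day, and it assumes first-order elimination at half-lives of 6 to 7.9 h. The number of patients affected is unknown and probably small. No test or decision rule depends on the PK summary, which is descriptive. The point is worth correcting because the line is wrong as it stands and cheap to repair, not because it threatens the trial's conclusions.

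**What to change.** Reconcile Appendix III with the Section 5.1 schedule:

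1. Tie the moved samples 2 to 9 to the second scheduled dose of Cycle 1, which is Day 8 on the current schedule, with the 24-hour draw on Day 9.
2. Add a row for the date and time of the dose actually sampled, and label samples 2 to 9 relative to that dose instead of the Day 1 dose. Align the pre-printed tube labels, or state how nominal times will be reconciled with the form.
3. For Part C, state how the moved draws fit with resection. Section 5.3.3 and Appendix III place surgery after the Day 8 dose and before Day 15, so the later moved draws could fall at the time of surgery, and sample 10 is also due just before it.

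This changes a sampling form and its labels, not dosing. The cost is a short correction in the next amendment. The Day 8 and Day 9 draws replace the Day 1 and Day 2 post-dose draws that would otherwise have been taken, so the planned PK sample count does not rise. The affected patient does need to be available for the 24-hour draw on Day 9. How to handle profiles when vomiting occurs later than 30 minutes is a separate question and need not hold up this correction.

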**APPENDIX IV-A: PHARMACODYNAMICS STUDY FORM- PLASMA PROTEINS**

COG Pt ID # \_\_\_\_\_ ACC # \_\_\_\_\_

Please do not write patient names on this form or on samples.

Cycle 1, Day 1 Date: \_\_\_/\_\_\_/\_\_\_/\_\_\_/\_\_\_ Dose Level: \_\_\_\_\_ mg/m^2 Dose Administered: \_\_\_\_\_ mg

Plasma samples (2 mL) will be collected for Plasma Protein studies on cycle 1, day 1, pre- and 4 hours after dose is given in consenting patients. Record the exact date and time each sample is drawn and the time of the selinexor administration.

Blood Sample No.	Time Point	Scheduled Sample Collection Time	Scheduled Selinexor Time Point	Actual Date Sample Collected or Dose Given	Actual Time Sample Collected or Dose Given (24-hr clock)
1	Cycle 1, Day 1	Prior to Dose on Cycle 1, Day 1		___/___/___	__:__:__
			Cycle 1, Day 1	___/___/___	__:__:__
2	Cycle 1, Day 1	4 hr after Day 1 dose		___/___/___	__:__:__

**Sample Processing Procedures:**

1. Ensure all tubes are labeled appropriately with site number, patient number and initials, and collection date prior to collection. Use a fine-point black permanent marker or lab marker to label tubes.
2. Collect 2 ml of blood into one BD Vacutainer tube for each time point. Be sure to use the correct tube for each time point.
3. Invert sample at least 8 to 10 times to ensure mixing of the EDTA and blood.
4. Immediately after collection place EDTA tube on ice or at 4°C for no longer than 30 minutes.
5. Centrifuge tube within 30 minutes of collection at 1000 g for 10 minutes at 4°C until red cells and plasma are separated by a well-formed polymer barrier.
6. Transfer the plasma sample equally, using a transfer pipette, into two cryogenic vials (Aliquot A and B). *Do not transfer the Buffy coat or any of the red cell pellet into the plasma sample as this will render the sample unusable for analysis.*
7. Immediately after transfer, the aliquots are stored at -70°C to -80°C.

**Sample Shipping Instructions:**

Batch and ship all Aliquots A for each patient together in the same shipment on dry ice to Karyopharm Therapeutics. Note: If samples for more than 1 patient are being shipped, samples must be grouped (e.g., separate boxes or paper sleeves for each patient). Retain Aliquot B samples until requested by Karyopharm Therapeutics to be shipped.

Shipment notification with tracking number should be emailed to [contact] and study assigned Research Coordinator along with a copy of this PD Study form.

If this form will be used as a source document, the site personnel who collected the samples must sign and date this form below:

Signature: \_\_\_\_\_

Date: \_\_\_\_\_

THIS PROTOCOL IS FOR RESEARCH PURPOSES ONLY, SEE PAGE 1 FOR USAGE POLICY

**APPENDIX IV-B: PHARMACODYNAMICS STUDY FORM- WHOLE BLOOD RNA**

COG Pt ID # \_\_\_\_\_ ACC # \_\_\_\_\_

Please do not write patient names on this form or on samples.

Cycle 1, Day 1 Date: \_\_\_/\_\_\_/\_\_\_/\_\_\_ Dose Level: \_\_\_\_\_ mg/m^2 Dose Administered: \_\_\_\_\_ mg

Whole blood RNA (two x 2.5 mL samples per time point) will be collected for gene expression analysis on cycle 1, day 1, pre- and 4 hours post dose administration. Record the exact date and time each sample is drawn and the time of the selinexor administration.

Blood Sample No.	Time Point	Scheduled Sample Collection Time	Scheduled Selinexor Time Point	Actual Date Sample Collected or Dose Given	Actual Time Sample Collected or Dose Given (24-hr clock)
1	Cycle 1, Day 1	Prior to Dose on Cycle 1, Day 1		___/___/___	__:__:__
			Cycle 1, Day 1	___/___/___	__:__:__
2	Cycle 1, Day 1	4 hr after Day 1 dose		___/___/___	__:__:__

**Sample Processing Procedures:**

1. Ensure PAXgene® Blood RNA Tube is at 18°C to 25°C prior to sample collection. To prevent contamination, the PAXgene® tube should be the last tube drawn for the correlative studies.
2. Allow at least 10 seconds for a complete blood draw to take place. Ensure that the blood has stopped flowing into the tube before removing the tube from the holder. The PAXgene® tube with its vacuum is designed to draw up to 2.5 mL of blood into one tube.
3. Collect 2.5 ml of blood into each of the two PAXgene® tubes required at every time point. Label tubes as Aliquot (A) and Aliquot (B).
4. Immediately after blood collection, gently invert the PAXgene® tube 8 – 10 times.
5. Store the PAXgene® tube upright at room temperature (18°C to 25°C) for a minimum of 2 hours and a maximum of 72 hours before transferring to a -20°C freezer.
6. When freezing samples, stand the PAXgene® tube upright in a wire rack. Do not freeze tubes upright in a styrofoam tray as this may cause the tubes to crack.
7. The PAXgene® tubes can be stored at -20°C and below. If tubes are to be kept at temperatures below -20°C, freeze them first at -20°C for 24 hours, then transfer them to -70°C or -80°C.

**Sample Shipping Instructions:**

Batch and ship all Aliquots A for each patient together in the same shipment on dry ice to Karyopharm Therapeutics. Note: If samples for more than 1 patient are being shipped, samples must be grouped (e.g., separate boxes or paper sleeves for each patient). Retain Aliquot B samples until requested by Karyopharm Therapeutics to be shipped.

Shipment notification with tracking number should be emailed to [contact] and study assigned Research Coordinator, along with a copy of this PD Study form.

If this form will be used as a source document, the site personnel who collected the samples must sign and date this form below:

Signature: \_\_\_\_\_

Date: \_\_\_\_\_

THIS PROTOCOL IS FOR RESEARCH PURPOSES ONLY, SEE PAGE 1 FOR USAGE POLICY

**APPENDIX V: TISSUE STUDIES FORM (PART C ONLY)**

**COG Pt ID #** \_\_\_\_\_ **ACC #** \_\_\_\_\_ **Date:** \_\_\_\_\_

(Please do not write patient names on this form or on samples)

**Sample Labeling:** Samples should be labeled with the following information:

Protocol number: ADV1414	Institution: _____	Sample Date: _____
Site of Acquired Tissue: _____		
Tissue obtained at (check one option below):  Diagnosis  Relapse  Subsequent Resection/Biopsy		
Tissue sample is from a:  Resection    or  Biopsy		
Tissue Type:  Fresh Frozen Tissue  Formalin Fixed Tissue		
 Paraffin Embedded Tissue Block  Unstained Slides		

All blocks or slides must be labeled with the patient’s study registration number (COG Patient ID #), the study I.D. (ADV1414), and the sample collection date. Data should be recorded on this Tissue Studies Form, which must accompany the sample(s).

**Archived Tissue Samples:** Archived paraffin-embedded tissue must be available for any previous resections for that patient (approximately 20 unstained slides or tumor block). The blocks or slides of tumor material should be sent at room temperature via Federal Express. During the warmer months (June – August), it is advisable to ship the block(s) with a frozen gel ice-pack in order to prevent the melting of paraffin-embedded tissue blocks during transit. Ensure cold pack is not in direct contact with specimen.

**Tumor Biopsy Collected at Surgical Resection**

Tumor tissue will be obtained upon surgical resection during cycle 1 from Part C patients only. At least 500 mg of tumor tissue should be collected by standard surgical procedures. Approximately 0.5 ml will be fresh frozen with preservatives in 2 mL screw cap cryogenic vials, while the remainder will be preserved in 10% buffered formalin in 15 ml conical tubes.

- a. **Fresh (flash frozen) biopsy** (approximately 0.5 ml collected). Please collect in the 2 mL screw cap cryogenic vials. Please do not fill tube more than ~1/3 full (~0.6 ml). Biopsy samples should be stored frozen at or below -70°C until shipment. Frozen samples will be shipped on dry ice.
- b. **Formalin-fixed biopsy** (remainder of sample collected during surgery after collection of fresh non-preserved tissue). Biopsy samples that are fixed in 10% buffered formalin will be stored at 4°C at the study sites until shipment. Parafilm all tubes. Fixed samples will be batched and shipped at 4°C.

**Please ship specimens along with email notification (with a copy to the Research Coordinator) of sample shipment and tracking number to:**

 
• Archived Tissue Samples
 
• Formalin-Fixed Biopsy
 
	

 
• Fresh (flash frozen) Biopsy
 
	

One copy of this form should be uploaded into RAVE. If this form will be used as a source document, the site personnel who collected the samples must sign and date this form below:

Signature: \_\_\_\_\_ Date: \_\_\_\_\_  
(site personnel who collected samples)

THIS PROTOCOL IS FOR RESEARCH PURPOSES ONLY, SEE PAGE 1 FOR USAGE POLICY

**APPENDIX VI: SELINEXOR DOSING NOMOGRAM**

**Selinexor Dose Assignment: 35 mg/m^2  
(Dose Level -1)**

BSA (m^2)	Total Daily Dose (mg/day)
0.84-0.92	30
0.93-1.07	35
1.08-1.21	40
1.22-1.35	45
1.36-1.5	50
1.51-1.64	55
1.65-1.78	60
1.79-1.92	65
1.93-2.07	70
2.08-2.21	75
≥ 2.22	80

**Selinexor Dose Assignment: 45 mg/m^2  
(Dose Level 1)**

BSA (m^2)	Total Daily Dose (mg/day)
0.84-0.94	40
0.95-1.05	45
1.06-1.16	50
1.17-1.27	55
1.28-1.38	60
1.39-1.50	65
1.51-1.61	70
1.62-1.72	75
1.73-1.83	80
1.84-1.94	85
1.95-2.05	90
2.06-2.16	95
2.17-2.27	100
≥ 2.28	105

THIS PROTOCOL IS FOR RESEARCH PURPOSES ONLY, SEE PAGE 1 FOR USAGE POLICY

**Selinexor Dose Assignment: 55 mg/m^2  
(Dose Level 2)**

BSA (m^2)	Total Daily Dose (mg/day)
0.84-0.86	45
0.87-0.95	50
0.96-1.04	55
1.05-1.13	60
1.14-1.22	65
1.23-1.31	70
1.32-1.4	75
1.41-1.5	80
1.51-1.59	85
1.6-1.68	90
1.69-1.77	95
1.78-1.86	100
1.87-1.95	105
1.96-2.04	110
2.05-2.13	115
2.14-2.22	120
≥ 2.23	125

THIS PROTOCOL IS FOR RESEARCH PURPOSES ONLY, SEE PAGE 1 FOR USAGE POLICY

**APPENDIX VII: MEDICATION DIARY FOR SELINEXOR**

**COG Patient ID:** \_\_\_\_\_ **Acc#** \_\_\_\_\_ **Institution :** \_\_\_\_\_

Please do not write patient names on this form.

Complete each day with the time and dose given for selinexor. If a dose is not due or is accidentally skipped leave that day blank. *Make note of other drugs and supplements taken under the Comments section below.* Selinexor tablets should be swallowed whole. Selinexor should be taken with food. If a dose is vomited within 30 minutes of administration and there is visible evidence of the tablet, the dose should be repeated. If the tablet is not visible, or the dose is vomited later than 30 minutes after administration, the dose should not be repeated. The patient/caregiver should make a note of if there is visible evidence of tablet on the pill diary and proceed with the next dose at the next scheduled time of administration. Add the dates to the calendar below and return the completed diary to your institution after each treatment cycle.

EXAMPLE	Date	Time	Number of Selinexor tablets		Comments
			10 mg	25 mg	
Day 1	1/15/14	8:30 AM	2	1	He felt nauseated an hour after taking the drug but did not vomit.
Cycle #:	Selinexor Dose: _____ mg		Start Date:	/ /	End Date: / /
Day	Date	Time	10 mg	25 mg	Comments
Day 1		Selinexor: _____			
Day 2					
Day 3					
Day 4					
Day 5					
Day 6					
Day 7					
Day 8		Selinexor: _____			
Day 9					
Day 10					
Day 11					
Day 12					
Day 13					
Day 14					
Day 15		Selinexor: _____			
Day 16					
Day 17					
Day 18					
Day 19					
Day 20					
Day 21					
Day 22		Selinexor: _____			
Day 23					
Day 24					
Day 25					
Day 26					
Day 27					
Day 28					

